## 1.0 STUDY OBJECTIVE(S)

To evaluate the ocular safety, tolerability, and efficacy of topical administration of ISV-305 (0.1% dexamethasone in DuraSite® 2 ophthalmic solution) compared with DuraSite 2 Vehicle when dosed twice daily (BID) for 1 day prior to surgery, the day of surgery, and 14 days post cataract surgery.

#### 2.0 STUDY DESIGN

This study is a Phase 3, randomized, multicenter, double-masked, vehicle-controlled, parallel-group clinical trial. Approximately 240 subjects will participate in the study and will be randomized in a 2:1 ratio to the ISV-305 group (160 subjects) and the vehicle group (80 subjects).

Written informed consent will be obtained from all subjects prior to any study-specific procedure. Subjects will be enrolled into a 16-day dosing phase, followed by a 2-week evaluation phase. There will be 7 visits scheduled during the study: a screening visit between 2 and 14 days prior to surgery; 3 visits during the dosing phase (Day 0 [Surgery Day], Day 1, and Day 8); and 3 visits during the evaluation phase (Day 15, Day 18, and Day 29). In addition, there will be a telephone call on Day -3 to remind subjects to begin dosing on Day -1, the day before surgery. Subjects will instill 3 doses prior to surgery (2 doses on Day -1, and 1 dose on Day 0 prior to surgery), 1 dose in the evening after surgery and continue dosing BID for 14 days after surgery.

Subjects will be randomized and receive instructions for dosing at home and completing a pain and dosing diary. Subjects will be cautioned to dose only for the specified amount of time. One bottle of investigational product (IP) will be dispensed to the subject, and a second bottle will remain at the site as a precaution only in the event of loss, etc., and will not be dispensed unless necessary. Throughout this protocol, the surgery eye is referred to as the study eye, and the fellow eye is referred to as the non-study eye.

All ratings and procedures should be performed by the same examiner from visit to visit whenever possible. Additional exams may be scheduled as necessary to ensure the safety of the subjects during the study period.

Subjects who terminate use of IP for any reason will be withdrawn from the study, the reason(s) clearly described on the subject's electronic Case Report Form (eCRF) and source documents, and the sponsor or designee will be notified.

If the investigator determines lack of efficacy during the dosing period, administration of a rescue medication (i.e., another medication to treat ocular inflammation and/or ocular pain in the surgery eye [study eye]) must occur after subject is withdrawn from the study, and be clearly documented on the source documents and the designated eCRF.

All adverse events (AEs), regardless of severity, will be followed throughout the study to the final study visit, until they resolve or resolve with sequelae (as judged by the investigator). Ongoing AEs will be followed beyond the final study visit at the discretion of the investigator and recorded in the source documents.

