#### 3.1 Inclusion Criteria

The following are inclusion criteria for prospective study subjects to be confirmed at Visit 1 (Day -14 – Day -2) prior to randomization. The sponsor will not grant any protocol eligibility waivers.

- a. Are  $\geq$  17 years of age at Visit 1 (Day -14 Day -2) prior to randomization, of either sex and any race, and scheduled for uncomplicated unilateral cataract surgery (phacoemulsification or extracapsular extraction) with posterior chamber intraocular lens implantation
- b. Signature of the subject or parent(s) or legally authorized representative on the Informed Consent Form (ICF), and when appropriate the minor's assent in accordance with local regulations
- c. Are willing and able to follow all instructions and attend all study visits
- d. Are willing to avoid disallowed medication for the duration of the study
- e. If female is of childbearing potential, agree to and submit a urine sample for pregnancy testing (prior to enrollment and at the end of the study), and use effective contraception for the duration of the study
  - Male subjects whose female partners are not post-menopausal must agree to one of the following: 1) completely abstain from sexual intercourse, 2) use a barrier method (condoms) with spermicide during sexual intercourse for the duration of the study, 3) provide documentation for having had a vasectomy (with documented infertility)
- f. Have best corrected visual acuity (BCVA) of +1.0 log of the minimum angle of resolution (logMAR -Snellen equivalent of 20/200) or better in the fellow eye (non-study eye)
- g. Able to self-instill the IP (or have a caregiver available to instill all doses of the IP, as instructed)
- h. Have an intraocular pressure (IOP) of > 8 mmHg and  $\le 22$  mmHg in the surgery eye (study eye)

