**Table 1: Schedule of Assessments** 

	Screening/ Randomization Phase	Dosing Phase (16 Days)				Evaluation Phase (15 Days)		
Evaluation 	Visit 1 Day -14 to Day -2	Phone Call Day -3 (±1)	Visit 2 Day 0 (Day of Surgery)	Visit 3 Day 1 (+1)	Visit 4 Day 8 (±1)	Visit 5 Day 15 (+1)	Visit 6 Day 18 (-1/+2)	Visit 7 Day 29 (± 2)
Written Informed Consent	X							
Demographics	X							
Entry Criteria	X							
Medical/Medication History	X							
Urine Pregnancy Test	X							X
Slit Lamp Biomicroscopy 	X			X	X	X	X	X
Visual Analog Scale	X			X	X	X	X	X
Intraocular Pressure	X			X	X	X	X	X
Best Corrected Visual Acuity	X			$X^3$	X	X	X	X
Ophthalmoscopy 	X					X	X 	X 
Confirm and Document Subject Eligibility	X							
Randomization	X							
Dispense IP and Pain/Dosing Diary	X							
Instruct Subject on IP and Dosing/Pain Diary	X							
AE Assessment	X	X	X	X	X	X	X	X
Dosing Reminder Call		X						
Update Concomitant Medications			X	X	X	X	X	X
Review Pain/Dosing Diary			X	X	X	X	$X^4$	X 
Collect IP						X	X 	X 
Collect Pain/Dosing Diary							X	X 
Exit Subject From Study			_					X

IP = Investigational Product; AE = adverse event; eCRF = electronic case report form

<sup>1All eye exams are to be conducted in the study eye only. The fellow eye (non-study eye) may be examined at the investigators' discretion.

<sup>2Performed by a board-certified ophthalmologist.

<sup>3A pinhole test may be employed at Day 1 (Visit 3).

<sup>4Dosing terminates on Day 14. Pain is assessed through the evening of Day 17.

<sup>5If not completed at previous visit.

Note: Unscheduled visits may occur during the study period. All assessments will be recorded on the eCRF for unscheduled visits, but it is up to the investigator which assessments to conduct. If the subject exits early, all Visit 7 assessments should be conducted, including ophthalmoscopy if not obtained at Day 15 (Visit 5).

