#### **6.2** Examination Procedures

The following ophthalmic examinations will be conducted in the surgery eye (study eye) at intervals specified in Table 1, The Schedule of Assessments. The fellow eye (non-study eye) may be examined at the investigators' discretion.

- **Best Corrected Visual Acuity (BCVA):** BCVA will be measured at every visit except Visit 2 (Surgery; Day 0). The Early Treatment Diabetic Retinopathy (ETDRS) log of the minimum angle of resolution (logMAR) will be used to measure BCVA.
- Intraocular Pressure (IOP): IOP will be measured at every visit except Visit 2 (Surgery; Day 0) in mmHg using an applanation tonometer.
- **Ophthalmoscopy**: Ophthalmoscopy will be performed at Visit 1 (Day -14 to Day -2) and Visit 5 (Day 15) by a board-certified ophthalmologist.
- **Biomicroscopy:** Slit lamp biomicroscopy, including the evaluation of ACC and anterior chamber flare (ACF), chemosis, bulbar conjunctival injection, ciliary injection, corneal edema, and keratic precipitates will be conducted by a board-certified ophthalmologist at every visit except Visit 2 (Surgery; Day 0).
- Visual Analog Scale (VAS): Eye pain/discomfort and photophobia will be evaluated at every visit except Visit 2 (Surgery; Day 0) using a Visual Analog Scale (VAS), scoring from 0 to 100 using a mark on a 100 mm line (0 = absent; 100 = maximum).
- Pain assessment via diary (Pain Diary): Surgery eye pain will be evaluated prior to each IP dose using a pain scale included in the pain and dosing diary that subjects complete at home.

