## 7.4 Follow-up of Adverse Events and Serious Adverse Events

All AEs, regardless of severity, will be followed throughout the study to the final study visit, until they resolve or resolve with sequelae (as judged by the investigator).

At the final study visit, new AEs, as well as follow-up information for continuing AEs, will be recorded in the eCRF and source document. Non-serious ongoing AEs will be followed beyond the final study visit at the discretion of the investigator and recorded in the source documents.

If an SAE is unresolved at the final study visit, it will be followed by the investigator until it resolves or resolves with sequelae (as judged by the investigator). Follow-up data for such SAEs will be recorded in the source document and reported to the sponsor or designee.

Subjects withdrawn from the study due to an AE or SAE will be followed by the investigator until the outcome is determined (resolved or resolved with sequelae) and, where appropriate, additional written reports and documentation will be provided to the sponsor.

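### Stopping IP early ends all scheduled visits, so early stoppers have one exit examination and, unless it falls in the Day 15 window, no Day 15 ACC

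*Protocol*

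**What the plan says.** Protocol Section 2.0 sets the rule: "Subjects who terminate use of IP for any reason will be withdrawn from the study". The reason must be recorded on the eCRF and in the source documents. For lack of efficacy during dosing, the same section says that rescue "must occur after subject is withdrawn from the study, and be clearly documented". Rescued subjects therefore leave the study too.

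The note under Table 1 (Section 6.1) gives early leavers one examination: "If the subject exits early, all Visit 7 assessments should be conducted". In Table 1, Visit 7 includes slit lamp, VAS, IOP and BCVA, and Section 6.2 makes ACC part of the slit-lamp examination. Section 7.4 adds that subjects withdrawn because of an AE or SAE "will be followed by the investigator until the outcome is determined".

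The endpoints are tied to visits. Section 8.1 takes ACC grade 0 at Day 15. Section 8.2 takes a VAS pain score of 0 at Days 1, 8, 15, 18 and 29. Section 8.3 takes BCVA, IOP and other ocular measures, with change from baseline, at each scheduled visit. Table 1 allows the Day 15 visit a window of +1 day.

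**The concern.** Footnote 4 to Table 1 states: "Dosing terminates on Day 14". Anyone who stops IP prematurely therefore stops before the primary visit. Because stopping IP also ends study participation, the Day 15 ACC is not collected unless the exit examination happens to fall in the Day 15 window.

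The matter cannot simply be left to the SAP. The SAP decides how a subject without a Day 15 value is counted, but it cannot supply the value. The subjects whose status stays open are those who stop without rescue, for example because of an adverse event, poor tolerability or a personal reason. An ACC grade taken at exit some days earlier is partial evidence and may differ from the Day 15 grade.

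The scheduled safety series ends at exit as well. Section 7.2 defines some AEs by measurement (an IOP rise of at least 10 mmHg, a BCVA loss of 3 lines or more). A change of that kind that first arises after exit has no scheduled measurement to show it.

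**Working it through.** **Step 1: the passages side by side.** Section 2.0 ends participation when IP stops. The Table 1 note supplies one exit examination. Section 7.4 supplies outcome follow-up for AE and SAE withdrawals, with no scheduled ocular examinations attached. No section asks subjects who have stopped IP to attend Days 15, 18 or 29. The passages agree with one another, so the point concerns the rule and not a contradiction.

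**Step 2: what the schedule loses.** There are five post-surgical assessment visits: Days 1, 8, 15, 18 and 29.
- Stop and exit after Day 8 but before the Day 15 window: 3 of 5 are lost (Days 15, 18, 29).
- Stop and exit between Day 1 and Day 8: 4 of 5 are lost.

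In each case one exit examination stands in their place.

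**Step 3: an illustration of size.** The protocol gives no figure on this point to reproduce. The only inputs from the document are the arm sizes, 160 and 80 (160 + 80 = 240). Everything else is assumed. Rates are given as ISV-305/vehicle.
- True Day 15 ACC-0 proportion p = 40%/20%, a difference of 20.0 points.
- Rescued fraction r = 5%/15%, all scored as failures: 8 + 12 = 20 subjects.
- Unrescued stoppers u, as a fraction of each arm, varied below.

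Clearing among unrescued subjects is c = p/(1 − r): 0.40/0.95 = 42.1% and 0.20/0.85 = 23.5%.

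Two illustrative ways of handling unrescued stoppers can each miss the true difference:
- **A.** They are scored as failures but would have cleared at rate c. The arm proportion becomes p − u·c.
- **B.** They are left out but were all failures. The arm proportion becomes p/(1 − u).

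| u (ISV-305/vehicle) | No Day 15 value | A | B |
|---|---|---|---|
| 5%/5% | 8 + 4 = 12 of 240 (5%) | 37.9 − 18.8 = 19.1 | 42.1 − 21.1 = 21.1 |
| 10%/5% | 16 + 4 = 20 of 240 (8%) | 35.8 − 18.8 = 17.0 | 44.4 − 21.1 = 23.4 |
| 5%/10% | 8 + 8 = 16 of 240 (7%) | 37.9 − 17.6 = 20.2 | 42.1 − 22.2 = 19.9 |

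Proportions are in percent and differences in percentage points, taken before rounding. The counts are of unrescued stoppers only. The shift from 20.0 is about 1 point in the first row, 3.0 or 3.4 in the second, and 0.1 or 0.2 in the third. It can go either way.

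**The case against.** The strongest reply is that the rule is coherent and may suit the target of the trial. Section 8.1 does not say that Day 15 ACC is wanted regardless of stopping IP. If the SAP counts stopping as failure, no Day 15 value is needed for these subjects on the primary endpoint, and the column A figures are then the target and not a distortion of it. This stands, and it limits the point to analyses that need Day 15 status after stopping. It does not cover the VAS endpoints in Section 8.2 or the safety measures in Section 8.3, whose later scheduled values are lost in any case.

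It can also be said that little is lost. The exit examination records ACC, VAS, IOP and BCVA, AE and SAE withdrawals are followed to outcome, and unscheduled visits are possible. The first two are real safeguards. A reader might infer that outcome and safety follow-up are lost altogether, and the documents do not support that. Unscheduled visits, however, have discretionary content and may not reach subjects who have already left.

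Two further inferences go too far:
- Inclusion criterion d ("Are willing to avoid disallowed medication for the duration of the study") might seem to conflict with rescue or with staying in the study afterwards. It concerns willingness, confirmed at Visit 1, and later rescue does not breach it. It needs no change.
- Dates of stopping and of rescue might seem to go unrecorded. The eCRF is not shown, Section 2.0 requires rescue to be documented, and Table 1 has the dosing diary and concomitant medications reviewed at visits. No gap can be claimed.

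**Conclusion.** The point holds as a design choice that loses data at small saving. Early stoppers have no scheduled Day 15 ACC unless exit falls in the Day 15 (+1) window, and no scheduled VAS, IOP or BCVA after the exit examination. That reading of the protocol is firm.

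The consequence for the result is not firm. The protocol gives no stopping, rescue or clearing rates, and the illustration rests wholly on assumed ones. There the shift runs from almost nothing to 3.4 points, and the largest values need twice the rate of unrescued stopping on ISV-305 as on vehicle. A reader might infer that the primary comparison is biased, or biased in a known direction. The documents support neither: the direction changes with the pattern of stopping and with the scoring, and calling any figure a shift presumes that the target is Day 15 ACC regardless of stopping. For rescued subjects the loss matters little if the SAP scores them as failures, which the protocol itself does not state.

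**What to change.** The change concerns data collection only.
- In Section 2.0 and the Table 1 note, separate two statuses: discontinued IP and withdrawn from study. Keep subjects who stop IP in the remaining scheduled visits, at least Days 15, 18 and 29, unless they withdraw consent. The note should say which status triggers the exit examination.
- Reconcile the wording of the Section 2.0 rescue sentence with these two statuses, because it is now expressed relative to study withdrawal. When IP is stopped and when rescue is given should not change.
- Leave the scoring of early stoppers and rescued subjects to the SAP.

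The cost is a short protocol amendment, with no new procedures and no added subjects. The downsides are extra attendance at already planned visits for a minority, and post-rescue values that reflect another treatment, so the SAP must say how they are used.

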## 7.3 Reporting and Evaluation of AEs and SAEs

Table 2 presents the reporting guidelines for AEs and SAEs. It is important that the investigator comply with the SAE reporting timelines in order to assure that safety reporting timelines of IRB/IEC and regulatory authorities such as the FDA can be met.

**Table 2:** Requirements for Reporting Adverse Events and Serious Adverse Events to Sponsor

Туре	Reporting Time	Type of Report
Serious	Within 24 hours	Adverse Event Report (AE eCRF) Serious Adverse Event Report Form
Non-serious	Per eCRF submission procedure	Adverse Event Report (AE eCRF)

All information relevant to the SAE must be recorded on the appropriate SAE Report Form, and the form submitted immediately (within 24 hours of learning of the event) to the sponsor Medical Monitor or designee:

The investigator must also provide sponsor or designee a copy of all pertinent medical records such as source documents, hospitalization records, death certificates etc. that are de-identified and contain only the study subject number and the subject initials. The investigator should maintain a copy of these medical records in his/her files, as well as any information and medical judgments from colleagues or other medical personnel who assisted in the treatment and follow-up of the subject.

The investigator should ensure that the subject receives appropriate medical treatment and follow-up. Subjects should receive follow-up until the SAE resolves or resolves with sequelae (as judged by the investigator).

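### Does Section 2.0 leave follow-up of unresolved serious adverse events to discretion, against Sections 7.3 and 7.4?

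*Protocol*

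**What the plan says.** Section 2.0 says that all adverse events (AEs), whatever their severity, are followed to the final study visit. It then adds: "Ongoing AEs will be followed beyond the final study visit at the discretion of the investigator and recorded in the source documents". It does not mention SAEs and does not refer to Section 7.

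Section 7.4, which deals with follow-up of AEs and SAEs, treats three situations separately:

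- Non-serious events: "Non-serious ongoing AEs will be followed beyond the final study visit at the discretion of the investigator and recorded in the source documents".
- SAEs: "If an SAE is unresolved at the final study visit, it will be followed by the investigator until it resolves", or resolves with sequelae. It adds: "Follow-up data for such SAEs will be recorded in the source document and reported to the sponsor or designee".
- Events that led to withdrawal: "Subjects withdrawn from the study due to an AE or SAE will be followed by the investigator until the outcome is determined", and "where appropriate, additional written reports and documentation will be provided to the sponsor".

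Section 7.3 agrees with Section 7.4 on SAEs: "Subjects should receive follow-up until the SAE resolves or resolves with sequelae". It also obliges sites to send records: "The investigator must also provide sponsor or designee a copy of all pertinent medical records".

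**The concern.** Under Section 7.1 an SAE is a kind of AE. The AE definition is broad, the list of serious outcomes itself speaks of life-threatening and sight-threatening AEs, and Table 2 in Section 7.3 sorts events into serious and non-serious. Read with those definitions, the Section 2.0 sentence takes in SAEs. It leaves their follow-up after the final visit to the investigator and names only the source documents as the place of record. Section 7.4 makes the same follow-up mandatory and adds reporting to the sponsor or designee. No section says which prevails. A site working from Section 2.0 alone could stop following an open SAE and lose the information on resolution and sequelae. That would be unwelcome in a steroid trial whose objective names ocular safety first.

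A second question arises inside Section 7.4. A non-serious AE that caused withdrawal and is still open at the last visit fits both the discretionary sentence and the mandatory sentence on withdrawals. The situation can occur, because Section 2.0 withdraws any subject who stops investigational product for any reason.

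**Working it through.** No figure in the protocol depends on this point, so the check is a comparison of the text by type of event open at the final visit.

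| Event open at the final visit | Section 2.0 | Sections 7.3 and 7.4 | Can both be followed? |
|---|---|---|---|
| SAE | Discretionary; source documents | Followed until resolved or resolved with sequelae; source document and sponsor or designee | Yes |
| Non-serious AE, did not cause withdrawal | Discretionary; source documents | Discretionary; source documents | Yes, identical |
| Non-serious AE that caused withdrawal | Discretionary; source documents | General sentence discretionary; withdrawal sentence mandatory, with reports where appropriate | Yes |

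**SAEs.** Two instructions contradict each other in practice when obeying one breaks the other. Here an investigator who follows the SAE to its end and reports it has used the discretion that Section 2.0 gives. Naming the source documents as a place of record does not exclude a report to the sponsor, and Section 7.4 itself names both. The wording differs, but one course of action satisfies every section.

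**Non-serious AE, no withdrawal.** The sections agree.

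**Non-serious AE with withdrawal.** One Section 7.4 sentence is general (non-serious events still open). The other is specific (subjects withdrawn because of an event) and expressly names both AEs and SAEs. The usual reading takes the specific sentence as qualifying the general one. Following such a subject until the outcome is known again satisfies both.

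**What the difference could reach in the data.** The primary endpoint is read at Day 15. The secondary endpoints are read at Days 1, 8, 15, 18 and 29. The ocular safety parameters in Section 8.3 are tied to scheduled visits, the last being Visit 7 on Day 29 (± 2). The AE and SAE endpoints are incidences, and the reporting period in Section 7.1 ends at the final visit exam. An event open at that exam has already been counted, however long it is followed afterwards. The 24-hour SAE report in Table 2 runs from the site learning of the event and is also unaffected. What remains is the later outcome of an event already recorded.

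**The case for a change.** The strongest case for a change is that Section 2.0 cannot easily be confined to non-serious events. The sentence before it covers all AEs regardless of severity, and severity is not seriousness, so that phrase does not set SAEs aside. Section 7.4 needed the word *non-serious* to limit the discretion, and Section 2.0 lacks it. Nor does Section 7.1 fill the gap. Its provision on possibly related events after the reporting period concerns events that occur then, not events already open. The remedy would cost one cross-reference.

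Most of this stands as a description of the text: the Section 2.0 sentence is too broad beside Section 7.4. Two things weaken it. The protocol's usage is mixed, since Sections 7.3 and 7.4 name AEs and SAEs as separate items, so a reader could take Section 2.0 as the rule for ordinary AEs. More important, harm needs a site to act on a design overview and disregard both later sections that address SAEs.

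The extent should also not be overstated. Crossing seriousness with withdrawal gives 2 × 2 = 4 types, and one could say that Section 2.0 differs from Section 7.4 in 3 of them. That counts the single SAE difference twice. It also counts as a difference the withdrawal case, where Section 2.0 matches one of the two Section 7.4 sentences. The text supports one difference (SAEs), one agreement, and one overlap that reads naturally as a rule with an exception.

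**Conclusion.** The observation is accurate but calls for no change to the plan. Section 2.0 carries an incomplete summary sentence, and Sections 7.3 and 7.4 give the detail. All three can be followed together, and a site that does so already follows and reports open SAEs. The overlap inside Section 7.4 is an ordinary general rule with a specific exception, not a second defect.

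The effect on estimates, error rates, sample size, SAE incidence and reporting timelines is nil. The remaining risk is missing outcome data for an SAE still open at the last visit at a site that read Section 2.0 in isolation. Its frequency cannot be estimated from the protocol. This conclusion assumes that sites work from the whole protocol and take the dedicated follow-up section as refining the overview. Reconciling the wording would be an editorial matter for the sponsor, who decides the follow-up rule. This review takes no position on what that rule should be.
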